### 12.2. Adverse Events

Adverse events will be coded using MedDRA version 19.1.

An AE will be considered a treatment emergent adverse event (TEAE) if it begins or worsens in severity after the first dose of study treatment (including the dose for PK purpose). Partial AE

start dates will be imputed as detailed in [Section 9.2.3](#). If an AE start date is completely missing it will be considered a TEAE.

Summary tables will be based on TEAEs. The incidence of TEAEs will be presented using counts and percentages of subjects with TEAEs and tabulated by SOC and PT. SOC will be sorted in descending frequency and PT within SOC will be sorted by descending frequency based on the incidence of all subjects in the population. If a subject has multiple occurrences (start and stop) of an event associated with a specific SOC or PT within a SOC, a subject will only be counted once in the incidence count for the SOC or PT within SOC respectively.

An overall summary table of AEs will be presented detailing the number and percentage of subjects for the following categories. One additional overall summary of AEs by disease categories instead of Cycle 1 total dose with the same AE categories below will also be presented.

- At least one TEAE;
- At least one Treatment-Related TEAE;
- At least one Grade  $\geq 3$  TEAE
- At least one Grade  $\geq 3$  Treatment-Related TEAE;
- At least one Serious TEAE;
- At least one Serious Treatment-Related TEAE;
- At least one Serious AE Occurred Prior to First Dose
- At least one TEAE leading to Treatment Withdrawn;
- At least one Treatment-Related TEAE leading to Treatment Withdrawn;

Except for all TEAEs which will be summarized by SOC and PT, the incidence of all other TEAEs by PT will be presented for the following in descending frequency based on the incidence of all subjects in the population.

- All TEAEs;
- Treatment-related TEAEs;
- TEAEs with Grade  $\geq 3$ ;
- Treatment-related TEAEs with Grade  $\geq 3$ ;
- Serious TEAEs;

- Treatment-related serious TEAEs;
- Serious AEs Occurred Prior to First Dose
- TEAEs leading to Treatment Withdrawn
- Treatment-related TEAEs leading to Treatment Withdrawn

A Treatment related AE is defined as an AE for which the investigator classifies the relationship to study treatment as being “Highly probable”, “Probable”, or “Possible” on Adverse Event eCRF. Missing relationship and toxicity grade will be imputed per [Section 9.2.3](#).

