3 TRIAL DESIGN

3.1 CLINICAL TRIAL OBJECTIVES AND ENDPOINTS

3.1.1 PRIMARY OBJECTIVES AND ENDPOINTS

Primary objectives	Endpoints
To establish the safety profile of SRA737	Safety parameters (referencing National Cancer Institute – Common Terminology Criteria for Adverse Events [NCI-CTCAE] v4.03) including: incidence, seriousness, severity and causality of each AE to SRA737, timing of AE onset, AE duration, and AEs leading to interruption, modification, or discontinuation of study treatment, and primary reason for discontinuation of study treatment if other than disease progression (PD), laboratory (eg, clinical chemistry, hematology, urinalysis) and vital sign data
To determine the MTD with 1 or more schedules of administration of SRA737	The highest dose at which $\leq 33\%$ of subjects have a dose limiting toxicity (DLT) in a cohort of up to 6 subjects
To propose a recommended Phase 2 dose and schedule of SRA737	A safe and well tolerated dose and schedule that provides high exposure, based on all available PK, PDn, and safety parameter data from all cycles of therapy
To evaluate the preliminary efficacy of SRA737 including efficacy in prospectively-selected genetically-defined subjects enrolled into indication-specific expansion cohorts	Objective response rate (ORR) Disease control rate (DCR) Time to response (TTR) Duration of response (DOR) Progression-free survival (PFS) Time to progression (TTP) Overall survival (OS)

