3.5 DEFINITION OF MAXIMUM TOLERATED DOSE AND RECOMMENDED PHASE 2 DOSE AND SCHEDULE

If 2 out of up to 6 subjects at the same dose level experience a DLT, as defined above, the MTD will be determined as a lower dose level for that schedule.

The RP2D and schedule will be defined at the end of the study and will take all clinically relevant toxicity, PK and PDn data into account. The RP2D will be a dose equal to or less than the MTD for the selected schedule.

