11.2.2 SAFETY

Safety data will be collected from the date of written informed consent. Safety variables will be summarized by descriptive statistics. Laboratory variables will be described using the NCI-CTCAE v4.03. The MTD for each schedule tested, if reached, and the RP2D and schedule will be described.

Treatment-emergent AEs will be reported for each dose level and coded using a current version of the MedDRA thesaurus, presented as tables of incidence of AEs by body system and by worst severity grade observed. Additional tables will be prepared to summarize incidence of AEs reported as related and unrelated events.

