### 9.3.2. Study Day and Duration

Study day is relative to the start date of the first treatment of the treatment phase. As stated above subjects may have the first dose for intensive PK purpose prior to the first treatment of the treatment phase. In such cases the study day will not align with the very first dose subjects received. It is set up this way to be consistent with the protocol “Day” definition and to avoid confusion in the listings when the study day is used. There is no study Day 0 defined.

- For an assessment that occurred on or after the study treatment:  
Study day = Date of assessment – date of first study treatment in treatment phase + 1
- For an assessment that occurred prior to the study treatment:  
Study day = Date of assessment – date of first study treatment in treatment phase

A duration between any two dates (such as AE duration) expressed in days will be calculated using the following conventions: Duration = later date – earlier date + 1.

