### 12.3. Laboratory Evaluations

Biochemistry and hematology laboratory tests are scheduled to be collected before the first dose for PK, at Day 1, 8, 15, and 22 for each cycle (frequency could be reduced at later cycles), and at the safety follow-up (30 days after the last dose). Troponin T or I are collected before the first dose for PK, Day 1 and Day 8 of Cycle 1 and Day 1 of Cycle 2 and Cycle 6, and at the safety follow-up. Urinalysis is collected before the first dose for PK, Day 1 of each cycle, and at the safety follow-up.

All continuous laboratory parameters in biochemistry and hematology will be summarized descriptively by actual value at each scheduled visit and the corresponding changes from baseline. The maximum post-baseline and minimum post-baseline (including both scheduled and unscheduled results) will also be provided before the by-visit summary. All parameters will be summarized in SI units.

Shift tables from baseline to visit will be provided for hematology and chemistry parameters to display low, normal, high, and missing values by treatment group in a 3-by-3 contingency table. Denominators for percentages will be the number of subjects with non-missing data at the specific assessment and baseline.

Urinalysis results will only be provided in the listing.

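### AE onset timing and duration belong to the primary safety endpoint, but the SAP tabulates incidence only, in two starting-dose columns with ungraded laboratory shifts, and section 13 declares none of it

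*SAP*

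**What the plan says.** **Protocol.** Section 3.1.1 lists the components of the first primary endpoint, the safety profile, and they include "timing of AE onset, AE duration". The same section says the RP2D and schedule are to be "based on all available PK, PDn, and safety parameter data from all cycles of therapy". Section 3.5 adds: "The RP2D and schedule will be defined at the end of the study". On analysis, section 11.2.2 makes a general commitment to summarize safety variables descriptively, and then two specific ones: "Treatment-emergent AEs will be reported for each dose level" and "Laboratory variables will be described using the NCI-CTCAE v4.03". The AE tables it names are incidence by body system and worst grade, and incidence of related and unrelated events.

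**SAP.** Section 4.1 shortens the safety endpoint to AEs, laboratory tests and vital signs. Section 4 sends only secondary and exploratory endpoints to other reports, so primary safety stays in this plan. Section 12.2 states: "The incidence of TEAEs will be presented using counts and percentages of subjects with TEAEs and tabulated by SOC and PT". A subject counts once per SOC or PT however often the event starts and stops. Section 9.3.2 gives a day-count rule: "A duration between any two dates (such as AE duration) expressed in days will be calculated using the following conventions". Section 9.2.1 and Table 2 set the safety columns as Cycle 1 Day 1 total daily dose up to 800 mg, above 800 mg (BID included), and overall. For hematology and chemistry, section 12.3 plans shift tables "to display low, normal, high, and missing values by treatment group in a 3-by-3 contingency table".

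**The concern.** The SAP prepares the data and then does not tabulate them. It imputes partial AE start and end dates (section 9.2.3) and defines AE duration (section 9.3.2). Start dates are used to decide whether an event is treatment-emergent, and no planned table uses an end date or a duration.

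For this drug, timing carries information. The protocol names bone marrow as a likely target organ (section 2.6). Duration decides whether a Grade 4 neutropenia or thrombocytopenia is a DLT: more than 7 days (section 3.4). Section 5.2 gives time to onset and recovery of myelosuppression as an example of data that could favor another schedule.

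What is at stake is the final description of safety that accompanies the RP2D and schedule. The planned tables would say how many subjects had a Grade 3 or higher event recorded as an AE. They would not say when it began, how long it lasted, or at which dose level and schedule. Anyone needing that would have to rebuild it from listings whose columns the SAP does not specify.

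**Working it through.** **1. Count of tables and declared changes.** The AE tables in SAP Table 6 are 14.3.2.1.1 and 14.3.2.1.2 (2), and 14.3.2.2 to 14.3.2.11 (10), so 2 + 10 = 12. Tables giving onset timing: 0 of 12. Tables giving duration: 0 of 12. SAP section 13 has five changes: disease-type grouping, biomarkers not collected, the QTc endpoint, interim analyses, and the alternative response population. Changes covering onset, duration, dose columns or laboratory grading: 0 of 5.

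**2. Commitment against plan.**

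| Item | Protocol | SAP |
|---|---|---|
| AE onset and duration | In the primary endpoint (3.1.1); general descriptive commitment, but no named table (11.2.2) | Duration formula and AE listing; no table |
| TEAEs by dose | Each dose level (11.2.2) | Two starting-dose columns plus overall; one overview table by disease category instead |
| Laboratory description | CTCAE v4.03 (11.2.2) | Low/normal/high shifts, by-visit values, minimum and maximum rows |

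A single low category holds every grade of a low count. The minimum row shows how low the column went, but not how many subjects reached each grade.

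**3. What the planned tables cannot separate.** This uses assumed data. It shows that tables can match, not how likely that is. Take 20 subjects in one column with dosing continued. Neutrophils are 4.0 at baseline, 0.8 when low (assumed below the normal range) and 3.0 otherwise. All are 3.0 at Days 1 and 36. Counts are weekly, as in protocol 7.2.2 for Cycles 1 to 3, and any unscheduled count equals the nearest scheduled one.

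- Case A: two subjects low at Days 8 and 15; two others low at Days 22 and 29.
- Case B: one low at Days 8, 15, 22 and 29; one at Days 8 and 15; one at Day 22; one at Day 29.

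Both cases give, at each of the four visits, 2 of 20 low and mean (2 × 0.8 + 18 × 3.0)/20 = 2.78, SD 0.677. Both give 4 of 20 ever low and a mean minimum of (4 × 0.8 + 16 × 3.0)/20 = 2.56, SD 0.903. The maximum row is 3.0 in both. Baselines are equal, so the change and shift rows match as well. If the affected subjects' AE records carry the same grade and attributes, the AE tables also match, because each subject counts once.

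Now treat consecutive low weekly counts as one spell.

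- Shortest length of the longest spell (first to last low count, inclusive): A 15 − 8 + 1 = 8 days; B 29 − 8 + 1 = 22 days.
- Longest length (day after the last normal count to day before the next): A Days 2 to 21, or 16 to 35, = 20 days; B Days 2 to 35 = 34 days.

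So 8 to 20 days and 22 to 34 days sit behind identical planned rows. The two lower bounds depend on the one-spell assumption. If counts recovered between visits, they no longer hold.

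**4. Starting-dose columns.** The lower column runs from the 20 mg starting dose to 800 mg. Protocol 3.7 allows one dose-level increase per cycle, if there was no Grade 2 or higher related toxicity in the prior cycle and the sponsor approves. With the typical 25% to 75% spacing (protocol 3.3), two steps multiply the dose by 1.25² = 1.5625 to 1.75² = 3.0625. A subject starting above 800/1.5625 = 512 mg (25% steps) or 800/3.0625 = 261 mg (75% steps) could take more than 800 mg in Cycle 3 and still be counted in the lower column.

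**5. Time origin.** SAP study day runs from Cycle 1 Day 1, as section 9.3.2 openly states. Cycle 1 Day 8 is 7 days after Day 1, 11 days after a Day −4 PK dose and 14 days after a Day −7 PK dose. Study day therefore understates time since a PK dose by 4 to 7 days, and an onset summary must name its origin.

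**The case against.** The strongest reply is that no promised table was dropped. Protocol 11.2.2 names only incidence tables for AEs, and section 13 is for changes from planned analyses. That stands for onset and duration: the departure there is from the endpoint definition and the general commitment to descriptive summaries. It does not answer the dose columns or the laboratory grading, which 11.2.2 specifies.

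Second, the data are reported per subject in the AE, SAE, DLT and hematology listings, and the by-visit rows show group-level timing. True, but a listing is not a summary of an endpoint. Unscheduled laboratory results are kept out of the by-visit rows (SAP 9.2.4) and reach only the minimum/maximum rows and listings.

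Third, decisions do not wait for the final tables. Cohort Review sees all AEs (protocol 3.3.1), trends are reviewed in real time (section 11), the section 5.2 schedule choice can be made at any time, and the RP2D draws on all available data. This stands. A reader might infer that dose escalation or the RP2D is compromised; the documents do not support that.

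Fourth, with cohorts of 1 or 3 to 6 subjects, a table split by dose and schedule will partly repeat the listing. This also stands, and it limits the gain.

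**Conclusion.** The point holds as a reporting gap. Part of a primary endpoint has no summary (0 of 12 AE tables). Two specific commitments in protocol 11.2.2, each dose level and CTCAE laboratory description, are replaced by coarser displays. None of the five section 13 changes declares any of this. The count rests on the visible list of output tables in SAP Table 6.

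Two stronger readings should be set aside. A reader might infer that a Grade 3 cytopenia with dosing continued would escape the AE tables. The documents do not show that. The AE list in protocol 10.1.1 is expressly not exhaustive, and protocol Table 2 recommends twice-weekly blood tests for Grade 3 neutropenia or thrombocytopenia when dosing continues, which may itself count as further investigation. A reader might also take the neutrophil example as evidence of how often spells would be misjudged. It is constructed data on laboratory counts, with recovery between weekly counts ruled out by assumption.

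The change is worth making because it is cheap. The trial's conduct and its escalation rules are not in question.

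**What to change.** - **SAP 12.2/12.3, one descriptive table.** Give time from first dose (including the PK dose) to first onset, and duration of the first episode with ongoing episodes flagged as censored. Cover treatment-related Grade 3 or higher TEAEs, and laboratory CTCAE v4.03 Grade 3 or higher neutropenia, thrombocytopenia and anemia including unscheduled counts. Show it by dose level and schedule at onset, pooling adjacent levels where cells are very small.
- **SAP 12.3.** Grade the hematology shift tables by CTCAE.
- **SAP section 13.** Declare the collapsed dose columns and the AEs whose onset and duration stay in listings. If the sponsor declines the new table, declare the whole omission.

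The cost is SAP wording, one table, regraded shift tables, one laboratory grading step and a link to dosing records. All inputs are already collected. The downside is sparse cells. Where only scheduled counts exist, timing is resolved to about 7 days in Cycles 1 to 3 and 14 days from Cycle 4 (protocol 7.2.2).

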All AEs, including SAEs, must be recorded in the eCRF for eligible subjects. All concomitant medications, including herbal medications and supplements must be recorded. Any therapy used to treat the event must be recorded. The eCRF will be reconciled with the safety database during and at the end of the trial. Therefore, the sites should ensure the data entered on the SAE report form and the data entered into the eCRF are consistent. The Sponsor or Sponsor's designee and the investigator(s) will regularly review the safety data from both the safety and the clinical database.

If known, the diagnosis of the AE or disorder should be recorded using standard medical terminology, rather than its individual symptoms. The following AE information must be included: dates of occurrence; severity; causal relationship; action taken; and outcome.

When possible, the NCI-CTCAE v4.03, definitions should be used to assess the severity of an AE.

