11.2 STATISTICAL ANALYSES

11.2.1 PRESENTATION OF DATA

Data will be presented in a descriptive fashion. Variables will be analyzed to determine whether the criteria for the trial conduct are met. This will include a description of subjects who did not meet all the eligibility criteria, an assessment of protocol deviations, IMP accountability and other data that impact on the general conduct of the trial.

Baseline characteristics will be summarized for all enrolled subjects.

Treatment administration will be described for all cycles. Dose administration, dose modifications or delays and the duration of therapy will be described.

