### 4.1. Primary Endpoints

- Safety parameters including adverse events (AEs), laboratory tests, and vital signs
- MTD: the highest dose at which  $\leq 33\%$  of subjects have a dose limiting toxicity (DLT) in a cohort of up to 6 subjects
- Recommended Phase 2 Dose (RP2D)
- Objective response rate (ORR)
- Disease control rate (DCR)
- Time to response (TTR)
- Duration of response (DOR)
- Progression-free survival (PFS)
- Time to progression (TPP)

- Overall survival (OS)

If there are no subjects with response (complete or partial response), TTR and DOR related summaries and listings will not be generated.

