### 12.1. Extent of Exposure and Compliance

Duration of treatment is defined as from the date of first dose in the treatment phase to the date of last dose taken from the SEA737 drug administration CRF page. If a subject only received the first dose for PK, the duration of treatment will be set to 1 day. In addition to the numeric summary of duration of treatment, the count and percentage of the following intervals will be presented:

- $\geq 4$  weeks
- $\geq 8$  weeks
- $\geq 12$  weeks
- $\geq 16$  weeks
- $\geq 20$  weeks

Cycle 1 compliance is used as part of the definition of the response evaluable population and will be summarized as numeric result and categorical result ( $\geq 75\%$  and  $< 75\%$ ). Cycle 1 compliance is from the SRA737 drug administration form for both QD and BID frequencies. For subject without compliance information on the CRF, the compliance will be calculated as follows:

Compliance = (Cycle 1 last dose date - first dose date + 1 - days when dose was not given) / 28  
 \*100%

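### The SAP summarizes treatment withdrawals but not dose interruptions, delays or reductions, or the AEs that led to them, although the protocol promises both, and SAP Section 13 does not declare the change

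*SAP*

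**What the plan says.** **Protocol.** Section 3.1.1 lists, within the first primary endpoint, "AEs leading to interruption, modification, or discontinuation of study treatment". The endpoint for the recommended Phase 2 dose (RP2D) in the same table draws on "safety parameter data from all cycles of therapy". Section 11.2.1, repeated in the synopsis, covers treatment administration in every cycle and adds: "Dose administration, dose modifications or delays and the duration of therapy will be described". Section 10.4 requires each AE record to carry "dates of occurrence; severity; causal relationship; action taken; and outcome".

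**SAP.** Section 4.1 shortens the safety endpoint to "Safety parameters including adverse events (AEs), laboratory tests, and vital signs". The overview in Section 12.2 has nine rows. Two concern action taken: "At least one TEAE leading to Treatment Withdrawn" and the treatment-related version. The by-term tables for action taken are 14.3.2.10 and 14.3.2.11, both on withdrawal. In Section 12.1, "Duration of treatment is defined as from the date of first dose in the treatment phase to the date of last dose taken", and "Cycle 1 compliance is used as part of the definition of the response evaluable population". Table 14.3.1 is the only exposure table. Section 13 lists five changes from the protocol; none concerns interruptions, modifications or dose delivery.

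**The concern.** SAP Section 4 sends secondary and exploratory endpoints to separate reports. Primary endpoints stay in this SAP, so a component of the primary safety endpoint that has no output here has no other announced home.

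The gap falls where the protocol expects dose action. Protocol Table 2 deals with marked toxicity first by considering an interruption, then by possible resumption at a lower level, and by discontinuation if there is no recovery after the permitted delay. A subject who is held, recovers and restarts need never enter a withdrawal row. Section 5.4 says a reduced dose should not be raised again, and Section 3.7 allows intra-subject escalation. SAP 9.2.1, however, fixes the safety columns by the Cycle 1 Day 1 dose. At stake is whether a reader of the report can tell that the dose at the head of a column was the dose subjects went on taking.

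**Working it through.** No stated sample size, power or error rate is involved. The check sets the promises beside the outputs, then applies the SAP's own definitions to one assumed subject.

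**Promise against planned output**

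| Protocol item | SAP summary |
|---|---|
| AEs leading to discontinuation (3.1.1) | Overview rows in 14.3.2.1.1 and 14.3.2.1.2; by-term Tables 14.3.2.10 and 14.3.2.11 |
| AEs leading to interruption (3.1.1) | None |
| AEs leading to modification (3.1.1) | None |
| Duration of therapy (11.2.1) | Table 14.3.1, first to last dose |
| Dose administration, all cycles (11.2.1) | Compliance in Cycle 1 only |
| Dose modifications or delays (11.2.1) | None |

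Two of the three named actions have no incidence output. The lists of tables, figures and listings in SAP Section 16 are present in full, so missing pages do not explain the gap.

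**What the exposure definitions show.** The subject is assumed, with figures chosen for arithmetic only and not taken from the documents: full dose on days 1–28, no dosing on days 29–56, half the dose on days 57–84. The hold is 56 − 29 + 1 = 28 days, which does not exceed the 28-day limit in Protocol 5.4.

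- SAP duration = last dose day − first dose day + 1 = 84 − 1 + 1 = 84 days = 12 weeks, so the subject counts in the ≥12-week band.
- Cycle 1 compliance by the SAP's fallback formula = (28 − 1 + 1 − 0)/28 = 100%.
- Share of days dosed = (28 + 28)/84 = 66.7%.
- Dose taken relative to the starting dose = (28 × 1 + 28 × 0.5)/84 = 42/84 = 50%.

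For a hold of h days from day 29 and a later dose fraction f, the relative dose over 84 days is [28 + f(56 − h)]/84:

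- h = 0, f = 1: 84/84 = 100%.
- h = 7, f = 0.75: (28 + 36.75)/84 = 77.1%.
- h = 28, f = 0.5: 50%.

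In all three cases Table 14.3.1 shows the same 84 days and the same 100%.

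The fallback formula counts days, not milligrams, so a reduction within Cycle 1 with every day dosed would also read 100%. The basis of the compliance figure taken from the CRF is not stated.

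**What still shows the toxicity.** SAP 12.2 counts TEAEs from the first dose with no Cycle 1 limit. The event behind the hold would appear in the TEAE tables and, at the severity that triggers action in Protocol Table 2, in the Grade ≥3 tables. What would not appear is that it led to a hold or a reduction.

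**The case against.** **A reader might infer that tolerability after Cycle 1 is not measured.** The documents do not support this. TEAEs, related TEAEs, Grade ≥3, serious and withdrawal TEAEs are tabulated over all cycles. Laboratory and vital-sign results are summarized by visit, with laboratory extremes that include unscheduled values. Treatment duration is banded to ≥20 weeks and discontinuation reasons are tabulated (SAP 10.1). Only dose action short of withdrawal is missing.

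**A reader might also infer that the report will make the drug look better tolerated than it was.** That needs a figure for how often intolerance appears as held or reduced doses rather than withdrawal, and the documents give none. What stands is that the tables cannot settle the question.

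**The Grade ≥3 tables already capture the triggers.** This is largely so. But Table 2 gives guidelines: it asks for an interruption to be considered and allows exceptions, and for Grade 3 neutropenia or thrombocytopenia it contemplates continued dosing with closer monitoring. The Grade ≥3 count includes events with no dose action, and it cannot separate those that led to one.

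**Listings are planned.** Listings 16.2.3.1 (exposure and compliance) and 16.2.3.2.1 (adverse events) may show dose changes and action taken. Their contents are not specified, and a listing gives no incidence. Protocol 11.2.1 promises only a description, and the AE tables in Protocol 11.2.2 are not broken down by action taken. That softens the shortfall, but the endpoint in 3.1.1 still names interruption and modification.

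**RP2D decisions do not rest on these tables alone.** This is correct. Cohort review uses all available data (Protocol 3.3.1), and the RP2D takes account of all clinically relevant toxicity (3.5). The consequence is for what the study report can demonstrate; the documents do not show that dose decisions were made blind to holds.

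**Conclusion.** The point holds as an undeclared departure from the protocol on part of the primary safety endpoint. Run as written, the SAP gives no incidence, in any cycle, of interruptions, delays or reductions, or of AEs leading to them. Treatment duration and Cycle 1 compliance cannot stand in for these: in the assumed subject they read 12 weeks and 100% while half of the starting dose was delivered over the period. That example shows what the definitions conceal; it does not estimate how often it happens.

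This should be corrected, but it does not undermine the safety analysis as a whole. The conclusion assumes that the output lists in SAP Section 16 are complete and that the unspecified listings do not contain incidence summaries.

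**What to change.** **SAP 12.2.** Add to Tables 14.3.2.1.1 and 14.3.2.1.2 the rows *TEAE leading to dose interruption/delay* and *TEAE leading to dose modification/reduction*, each all-cause and treatment-related: 2 × 2 = 4 rows per table. Add matching by-preferred-term tables, as is already done for withdrawal.

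**SAP 12.1 and Table 14.3.1.** Add, over all cycles, the number and percentage of subjects with at least one interruption or delay, and with at least one reduction. State that duration of treatment includes gaps.

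**Optional.** Relative dose intensity and counts of intra-subject escalation go beyond the protocol's promise. Relative dose intensity would need a defined planned-dose denominator that handles intra-subject escalation (Protocol 3.7) and alternative schedules (Protocol 5.2).

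**Minimum alternative.** Declare and justify the omission in SAP Section 13, and specify that Listings 16.2.3.1 and 16.2.3.2.1 show dose changes and action taken.

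**Cost.** SAP wording and several extra tables, with no new visits. Action taken is required on each AE record (Protocol 10.4), diary cards record missed doses (Protocol 7.2.2), and the SAP's fallback compliance formula already uses days without dosing. The coded categories of action taken and the fields on the drug-administration form are not visible in the documents, so their adequacy should be confirmed first. Tolerability may look less favourable once these counts are shown.
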